### **Sample size calculation**

The sample size calculation is based on a clinical superiority calculation using data from a pilot RCT by Kemp et al. Kemp et al. found a mean change of 27 (SD 26) points on the iHOT-33 in their strength exercise group (e.g., intervention group) and a mean change of 11 (SD 8) points in their stretching group (e.g., control group) after 12 weeks of intervention (between-group difference of 16 [95% CI -9; 38] points). The superiority margin is a 6 points MCID in the between-group change on the iHOT-33. The estimated mean difference of 16 points, a superiority margin of 6 points, a SD of 19.2, a power of 80% and an alpha level of 5% results in a total sample size of n=94 (n=47 in each group). After allowing a dropout-rate of up to 28% our required sample size will be n=120 (n=60 in each group).

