## **STATISTICAL PRINCIPLES**

### **Confidence intervals and p-values**

Results will be expressed as between-group differences in means with 95% confidence intervals.

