## **Analysis methods**

### **Primary analysis**

#### *Intention-to-treat analysis:*

The primary analysis of clinical effectiveness will be the assessment of the between-group mean difference in change in hip-related QoL (iHOT-33) from baseline to 6 months after randomization. Between-group mean differences in change larger than 6.1 points will be considered clinically relevant. Consequently, to determine the intervention's effectiveness compared to usual care, the lower limit of the 95% confidence interval for the mean difference must be greater than 6.1 points. Secondary analysis will be the assessment of the between-group mean difference in change in secondary outcomes from baseline to 3 months, 6 months, and 12 months. Assessment of between-group differences in changes will be conducted using a linear mixed-effect model for continuous variables and a generalized linear mixed-effect model for binary variables. This approach accounts for the correlation between repeated measurements within the same patient over time. The model will include fixed effects for the intervention group (physiotherapist-led exercise or usual care) and time points (Baseline, 3, 6, and 12 months). Patients and recruitment sites (Aarhus, Aalborg, Hvidovre, Horsens, or Melbourne) will be included as random effects to account for potential clustering effects. To assess whether the effect of the intervention on hip-related QoL (iHOT-33) varies over time, an interaction term between the intervention group and time will be included. Supplementary, to further guide the clinical interpretation of change in iHOT-33, the between-group difference in the proportion of participants achieving the minimal clinically important difference of 6.1 for within-patient score change was analyzed using an a-priori threshold of 20%. A difference of less than 20% was considered no meaningful difference between treatments, and 20% or greater was considered a meaningful difference. A sensitivity analysis for thresholds of 10% and 30% will be conducted. Supplementary to this interpretation, we will conduct calculations for other identified values of minimal important change by Scholes et al., of 8.7 points, and Kemp et al., of 10.0 points.

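### The supplementary 20% responder rule declares no meaningful difference from the estimate alone, even when the 95% CI still includes 20 points

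*SAP*

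**What the plan says.** The rule is in the SAP under Analysis methods, Primary analysis, Intention-to-treat analysis. It is introduced as a supplement to help interpret the iHOT-33 result clinically. It compares the arms on the proportion reaching a within-patient change of 6.1 points and then classifies the difference: "A difference of less than 20% was considered no meaningful difference between treatments, and 20% or greater was considered a meaningful difference". On robustness it adds: "A sensitivity analysis for thresholds of 10% and 30% will be conducted". Further calculations are planned at within-patient cut-offs of 8.7 and 10.0 points.

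For the mean difference, the same section requires that "the lower limit of the 95% confidence interval for the mean difference must be greater than 6.1 points".

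The general statement under Confidence intervals and p-values is: "Results will be expressed as between-group differences in means with 95% confidence intervals". It does not mention proportions. The intention-to-treat section does plan a generalized linear mixed-effect model for binary variables, but does not say whether responder status is one of them. The Table 2 shell has no responder row.

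The sample size section plans 47 evaluable and 60 enrolled patients per arm. It gives no expected responder rates. Its pilot source "found a mean change of 27 (SD 26) points on the iHOT-33 in their strength exercise group" and "a mean change of 11 (SD 8) points in their stretching group", both after 12 weeks.

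**The concern.** The two labels cover every possible value and meet at a single cut, so only one number, the observed difference, can be sorted this way. A result below 20 points becomes a statement that the treatments do not differ meaningfully. That is a claim of absence, and it needs an interval narrow enough to exclude 20 points. The rule does not ask for one. The other label also takes no account of sampling error, but a claim of absence is the more likely to mislead.

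At stake is how the trial is read clinically. A mean difference reported with due regard to its uncertainty could stand beside a firm responder statement, on the same outcome, that the data do not support.

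**Working it through.** **1. Inputs.** Responder cut-off 6.1 points and threshold 20%, read here as percentage points (intention-to-treat section). Arm sizes 47 and 60, pilot mean changes 27 and 11 with SDs 26 and 8, and planning SD 19.2 (sample size section). The planning SD follows from the pilot SDs: sqrt((26² + 8²)/2) = sqrt(370) = 19.24. The plan has no figure of its own for the responder rule, so response rates are assumed and shown as a range.

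**2. Precision.** Wald 95% half-width = 1.96 × sqrt[pC(1-pC)/n + pT(1-pT)/n].
- Both arms 50%, n=47: 1.96 × sqrt(0.50/47) = 0.202.
- Both arms 90%, n=60: 1.96 × sqrt(0.18/60) = 0.107.

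The half-width is therefore about 11 to 20 points, at its widest as large as the threshold.

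**3. Single results at 60 per arm.**
- 39/60 versus 30/60: difference 15 points; SE = sqrt[(0.65×0.35 + 0.50×0.50)/60] = 0.0892; CI -2 to 32. Label: no meaningful difference.
- 42/60 versus 30/60: difference 20 points; SE = 0.0876; CI 3 to 37. Label: meaningful.

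Three responders reverse the label although the intervals largely overlap. With 30/60 responders on control, the upper limit is below 20 at 31/60 (difference 1.7 points, upper limit 19.6) but not at 32/60 (upper limit 21.2). The rule declares absence for anything under 20. A Newcombe interval for the first example gives -2.6 to 31.4, so the choice of interval matters little.

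**4. Response rates implied by the planning figures.** P(change > 6.1) = 1 - Φ((6.1 - mean)/SD), assuming normal changes.
- SD 19.2 in both arms: control 1 - Φ(-0.255) = 0.601; exercise 1 - Φ(-1.089) = 0.862; true difference 26 points.
- SDs 8 (control) and 26 (exercise): control 1 - Φ(-0.613) = 0.730; exercise 1 - Φ(-0.804) = 0.789; true difference 5.9 points.

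**5. How often the label appears.** Exact sums over two independent binomials with Wald 95% CIs. The label is counted when exercise minus control is below +20 points. Each cell gives n=47; n=60.

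| Scenario (exercise vs control) | Labelled no meaningful difference | Of those, upper limit ≥20 | Whole CI within ±20 |
|---|---|---|---|
| SD 19.2: 86% vs 60% | 25%; 18% | 98%; 98% | 0.4%; 0.3% |
| 80% vs 60% (true difference exactly 20) | 51%; 46% | 95%; 94% | 2%; 2% |
| SDs 26/8: 79% vs 73% | 95%; 96% | 61%; 53% | 22%; 37% |
| Equal arms, 50% to 80% | 98-99%; 98-100% | 31-51%; 21-38% | 2-36%; 22-58% |
| Equal arms, 90% | over 99.9%; over 99.9% | 10%; 5% | 79%; 90% |

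Counting the equal-arm label on the absolute difference instead gives about 95 to 99% at response rates of 50 to 80%; the picture is unchanged.

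**6. The other thresholds.** Using 10 or 30 points moves the cut and repeats the same comparison. The half-width in step 2 does not change.

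**The case against.** The strongest reply is that the SAP never says intervals are ignored. The responder sentence could be read as stating only what size of difference matters, as the section does for the mean before adding a confidence-limit requirement. The planned mixed model for binary variables could also supply an interval, and a row missing from an illustrative table shell proves little. This stands in part: a reader might infer that the SAP rules out a CI for the responder difference, and it does not. But for responders no confidence-limit requirement follows the threshold, and a printed interval would not change the prescribed label.

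A second reply is that the label is often right. This is also true. With a true difference of 5.9 points or none it agrees with the truth, and when the truth sits exactly on the cut a rate near 50% is what any cut-point gives. Material mislabelling is concentrated in the SD 19.2 scenario, which rests on normality and 12-week pilot data. The documents do not support saying that the label would usually be wrong, only that it can be applied without support.

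Third, the analysis is supplementary and effectiveness is decided on the CI for the mean. That stands and limits the severity.

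**Conclusion.** The concern holds as a minor defect in a stated rule. Followed as written, the rule reports no meaningful difference for results that leave 20 points well inside the interval. How often depends on the true rates: among labelled trials, the share with an upper limit of 20 or more runs from about 98% (SD 19.2) down to 5 to 10% (both arms at 90%). These figures assume percentage points, independent binomial responses and 47 to 60 analysed patients per arm; the two scenarios derived from the pilot also assume normal changes. They are a range, not a forecast.

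Two stronger inferences are not supported. The primary conclusion is not affected, because it does not use this rule. Nor does the finding imply that a meaningful difference may be stated only when the whole CI lies at or beyond 20 points. That condition would be met in only 11 to 13% of trials under a true difference of 26 points, so it is a trade-off and not a correction.

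**What to change.** Amend the responder text in the intention-to-treat section as follows:
- Report the responder risk difference with its 95% CI at 6.1, 8.7 and 10.0 points. Table 2 is a natural place for it.
- State no meaningful difference only when the 95% CI lies within -20 to +20 percentage points.
- Otherwise describe the estimate as below, or at or above, the 20-point threshold. Where the CI includes 20, say that the result is inconclusive relative to it.
- Read the 10- and 30-point sensitivity thresholds against the same CI.

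The cost is a few sentences and no extra data; the primary analysis is unchanged. The downside is fewer firm statements of absence. At 20 points the last column of the table shows how many remain. At 30 points absence could be stated in 77 to 87% of trials (SDs 26/8) or about 7% (SD 19.2). At 10 points it could be stated in essentially none of the scenarios, except about 4 to 6% of trials if both arms respond at 90%. That is rare, but not impossible.

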## **Health Economic Evaluation**

Incremental cost-effectiveness (ICER) and cost-utility (ICUR) analyses will be conducted from both a societal and healthcare perspective to estimate the cost-effectiveness and cost-utility of supervised strength exercise compared to usual care. The time horizon will be 12 months. Costs will be expressed in Danish Crowns (DKK) (Price year 2026). The base-case cost-effectiveness analysis will follow the intention-to-treat principle. Findings will be reported following the Consolidated Health Economic Evaluation Reporting Standards (CHEERS) guideline.

### *Measurement of costs:*

Costs of the supervised strength exercise intervention will be estimated using micro-costing. We will identify, measure, and value direct costs associated with physiotherapist-led strength exercise. These include the time of the physiotherapist, facility, materials, and travel costs. Unit costs for physiotherapists will be identified using salaries from the Danish Association of Physiotherapists in Denmark and the Australian Physiotherapist Association in Australia. Costs in Australian Dollars (AUD) will be converted to DKK using the average purchasing power parity (PPP) exchange rate over the project period (i.e., 2023-2025).

Measurement of the number of physiotherapist-led strength exercise sessions will be done using the paper-based exercise diary completed by participants and validated by the physiotherapist delivering the intervention. The value of total costs will be the number of supervised sessions multiplied by the associated salary unit cost. Costs of usual care and other costs in the supervised strength exercise group will be measured using the HUQ questionnaire (e.g., costs related to healthcare and medication usage) and the iPCQ questionnaire (e.g., costs related to absenteeism and presenteeism of paid work, and productivity losses related to unpaid work). Costs will be summarized in Table 4.

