#### *Healthcare utilization questionnaire (HUQ):*

Healthcare utilization and medication usage are measured by a nine-item patient-reported cost questionnaire (HUQ) including visits to primary care physician and therapist, medical specialist, outpatient hospital care, hospital admissions, diagnostic tests, and medical procedures.

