### **Pre-specified exploratory analyses: Adherence and volume**

A pre-specified exploratory secondary analysis will investigate whether exercise session adherence (expressed as a % of supervised sessions and as a % of total prescribed sessions) and exercise volume are associated with strength exercise effectiveness on hip-related quality of life (e.g., iHOT-33, 0-100), maximal muscle strength (e.g., 1 RM unilateral leg press) and functional performance (e.g., One Leg Jump for Distance and One Leg Rise Test). Multiple linear regression will be applied in all analyses. With a rule of thumb of 10 observations (i.e., participants) per independent variable, and approximately 60 participants in the physiotherapist-led strength exercise group, we can include 6 independent variables (e.g., categories) in the regression model. The independent variables will be potential moderators measured at baseline and at 6-month follow-up that were expected to be associated with changes in the outcome (e.g., dependent variable). The dependent variable in each of the multiple linear regression models will be the change in the iHOT-33 score (0-100), maximal muscle strength (e.g., 1 RM unilateral leg press), and functional performance (e.g., One Leg Jump for Distance and One Leg Rise Test) from baseline to 6-month follow-up. The independent variables will be 1) Supervised exercise adherence (expressed as a % of maximal 12 sessions), 2) Total exercise adherence (expressed as a % of maximal sessions), 3) Volume, 4) Biological sex (Male/Female), and 5) Age at baseline. This analysis will be reported (Table 6) in a secondary paper with a clear reference to the primary paper.

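### The intervention cost is listed with four components but valued as supervised sessions times salary, travel is named for trial sessions only, and unsupervised sessions have no costing rule

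*SAP*

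**What the plan says.** All of the following is in the SAP.

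- **Measurement of costs, first paragraph.** The intervention is to be micro-costed. On the direct costs it says: "These include the time of the physiotherapist, facility, materials, and travel costs". Unit costs are sourced for physiotherapist salaries only.
- **Measurement of costs, second paragraph.** Sessions are counted from the exercise diary, and then: "The value of total costs will be the number of supervised sessions multiplied by the associated salary unit cost". Everything else comes from questionnaires: "Costs of usual care and other costs in the supervised strength exercise group will be measured using the HUQ questionnaire", together with the iPCQ for productivity.
- **Healthcare utilization questionnaire (HUQ).** Its nine items are described as covering medication and healthcare use, "including visits to primary care physician and therapist, medical specialist, outpatient hospital care, hospital admissions, diagnostic tests, and medical procedures". Travel is not named there, in the iPCQ section or in Table 4.
- **Health Economic Evaluation.** The analyses "will be conducted from both a societal and healthcare perspective". The SAP does not say which cost components enter which perspective.
- **Adherence and exercise volume; exploratory analyses.** The diary records whether each session was supervised. Two adherence measures are used: "Supervised exercise adherence (expressed as a % of maximal 12 sessions), 2) Total exercise adherence (expressed as a % of maximal sessions". The per-protocol set is defined by attendance above 75% of all sessions, not of supervised sessions.

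**The concern.** The two paragraphs on intervention cost cannot both be followed. One analyst would build a unit cost from time, premises, materials and travel. Another would multiply a session count by a salary. They would obtain different cost differences, and so different ICERs and ICURs, from the same data. Nothing in the SAP settles the choice before costs are seen.

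The coverage of the costing is also unsettled. Travel is mentioned for trial sessions and not for other visits. The SAP treats supervised and unsupervised sessions together as the treatment when it measures adherence, but has a valuation rule only for the supervised ones. Cost-effectiveness at 12 months is the trial's second hypothesis, so the cost difference is a main result. The economic sensitivity analyses named are complete-case and excluding Melbourne, with imputed datasets added in Table 5. None varies a cost component, so none would show how much depends on this choice.

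**Working it through.** The SAP gives no unit cost or expected cost, so there is no figure of its own to reproduce. The check sets the two readings against a common boundary.

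**Inputs**
- S, supervised sessions attended: at most 12 (exploratory analyses section).
- Total sessions: not stated. The eligibility item on willingness to train twice weekly for six months suggests 2 × 24 = 48 to 2 × 26 = 52. This is an assumption.
- t, travel cost per visit: not stated; DKK 50-200 assumed.
- V_E and V_U, other visits per participant in the exercise and usual-care arms: not stated.

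**Step 1: what each reading includes**

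| Component | List governs | Formula governs |
|---|---|---|
| Physiotherapist time, supervised sessions | yes | yes |
| Facility, materials | yes | no |
| Travel to trial sessions | yes | no |
| Travel to HUQ visits, both arms | not specified | not specified |
| Unsupervised sessions | no rule | no rule |

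**Step 2: travel in the incremental cost.** The last two lines take HUQ visits to be valued without travel, which the SAP does not state.
- Common boundary, travel on every visit: t × (S + V_E − V_U).
- List: t × S. Error against the common boundary: t × S − t × (S + V_E − V_U) = t × (V_U − V_E).
- Formula: 0. Error: −t × (S + V_E − V_U).

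**Step 3: numbers, with S = 12**
- List against formula: 12 × 50 = DKK 600 to 12 × 200 = DKK 2,400 per full attender, before facility and materials.
- Error under the list with V_U = V_E: 0.
- With six more usual-care visits: 6 × 50 = DKK 300 to 6 × 200 = DKK 1,200, counted against exercise.
- With three more other visits in the exercise arm: −3 × 50 = −DKK 150 to −3 × 200 = −DKK 600, counted in favour of exercise.
- Error under the formula with V_U = V_E: −DKK 600 to −DKK 2,400, so the incremental cost of exercise is too low.

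**Step 4: unsupervised sessions**
- Of 48: 48 − 12 = 36, and 36/48 = 75%.
- Of 52: 52 − 12 = 40, and 40/52 = 77%.

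On these assumed totals, about three quarters of the programme's sessions lie outside the stated formula. This is a share of sessions, not of cost.

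**The case against.** A reader might infer more: that travel is charged to exercise while every other visit is costed without it, so that the arms are compared on different cost boundaries and the result is tilted by arm. The documents do not support that, for four reasons.

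- The salary formula removes travel from trial sessions too, so on that reading travel is zero in both arms.
- That HUQ visits carry no travel cost is an inference from silence. The SAP gives no unit costs for these visits and describes the questionnaires' content by example. Travel could be added when the visits are valued.
- The HUQ and iPCQ are used in both arms. Any gap is between trial sessions and other visits, and it affects the comparison under the list only as far as other visits differ between arms. No expected visit counts are given.
- The SAP does not say whose travel is meant, or that every component enters both perspectives. It therefore does not show that patient travel is charged to the healthcare perspective.

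It is also fair to say that unsupervised sessions use no supervising physiotherapist's time and may cost little, and that facility and materials could include equipment supplied for them.

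These arguments rule out a claim of demonstrated bias in a known direction. They do not reconcile the list with the formula, and they supply no rule for unsupervised sessions.

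**Conclusion.** The point holds as an internal contradiction and an unsettled cost boundary, not as a proven bias between arms. The formula omits three components that the SAP itself calls direct costs. The list specifies travel for trial sessions alone. Under both, unsupervised sessions are part of the treatment and have no valuation rule. Neither reading gives a sound societal incremental cost.

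The size cannot be established from the SAP. The DKK amounts above show scale only and rest on assumed trip costs and visit differences. The session shares rest on an assumed total. A cost-per-QALY figure would need an assumed QALY gain as well, and none is offered. The point merits a change to the SAP before costs are analysed, because the choice affects a main result and is cheap to settle.

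**What to change.** In Measurement of costs:

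1. Replace the salary-only sentence with one formula that includes every listed component (physiotherapist time, facility, materials, travel), and give a unit-cost source for each.
2. Societal perspective: apply the same travel unit cost per visit to trial sessions and to HUQ visits in both arms. Value any facility or equipment cost of diary-recorded unsupervised sessions, or justify a zero cost.
3. Healthcare perspective: state which components enter, and leave out patient-borne travel.
4. Add a one-way sensitivity analysis that varies the travel and unsupervised-session unit costs.

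The cost is some wording and a few unit costs; visit counts and diary sessions are already planned for collection. The downside is that these unit costs would be standard or imputed values and not measured per participant, because the diary as described does not record venue or equipment.

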#### *Dropouts:*

In instances where patients are not satisfied with how their treatment is progressing before reaching their individual goal, they will be able to have an additional consultation with their treating surgeon, where they will be treated in their best interests. There is a risk of dropout in both groups if the treatment results in insufficient improvement of symptoms. Dropout and the reason for dropout will be recorded throughout the study.

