#### *Hip surgery*

The number of patients undergoing hip surgery in each intervention group will be recorded throughout the study and registered at 3, 6, and 12 months.

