### *Measurement of outcomes:*

In the cost-utility analysis, we will use Quality Adjusted Life Years (QALYs) to measure the impact of the healthcare intervention on participants' health-related QoL. QALYs provide a comprehensive and standardized metric that combines both the quantity and quality of life experienced by individuals. To calculate QALYs, we will employ the EQ-5D-5L questionnaire. Using a preference-based algorithm, we will convert EQ-5D-5L responses into a single utility index score, representing each participant's health-related quality of life.

QALYs will be calculated based on the utility index scores over the study period using Danish population norms. We will use linear interpolation between measurement points (baseline, 3 months, 6 months, and 12 months). In the cost-effectiveness analysis, iHOT-33 (0-100) total scores will be used. Outcomes will be summarized in Table 4.

*Base-case cost-effectiveness and cost-utility analysis:*

Missing data will be imputed using Multiple Imputation with Chained Equations (MICE). Cost and effect data will be assumed to be missing at random, which means that missing observations are explained by observed variables. The imputation model will include outcome variables and predictor variables that differ at baseline, are related to missing data, or are associated with the outcome. To account for the skewed distribution of cost data, predictive mean matching will be used in MICE. The number of imputed datasets will be increased until the loss of efficiency is less than 5%. Each of the imputed datasets will be analyzed separately. Results from the multiple datasets will be pooled using Rubin's rules. To account for the possible clustering of data, analyses will be performed using linear mixed-effect models. Accounting for the possible clustering of data at the hospital level is very important, as most economic evaluations fail to do so, whereas ignoring the possible clustering of data might lead to inaccurate levels of uncertainty and inaccurate point estimates.

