iHOT-33: International Hip and Outcome Tool 33. Symptoms: Symptoms and Functional Limitations. Sports and Recreational Activities. Job: Job-related concerns. Social: Social, Emotional, and Lifestyle Concerns. HAGOS-Sport: Physical Function in Sport and Recreation. 1 RM: 1 repetition maximum. Cm: centimeters. Kg: Kilograms. PASS: Patient Acceptable Symptom State. HAGOS: The Copenhagen Hip and Groin Outcome Score. SQUASH: the short questionnaire to assess health-enhancing physical activity. TSK-17: Tampa Scale of Kinesiophobia. HSAS: the Hip and Sports Activity Scale. RTS: Return to Sport questionnaire. SD: Standard Deviation. 95% CI: 95% Confidence Interval. MET: Metabolic Equivalent.							

**Table 4:** Costs and effects from baseline to 12-month follow-up in the intention-to-treat population.

	Physiotherapist-led exercise (n = )			Usual care (n = )			ICER/ICUR (95% CI)	
	Baseline (95% CI)	12-mo (95% CI)	Change (95% CI)	Baseline (95% CI)	12-mo (95% CI)	Change (95% CI)		
Effects								
QALYs								
iHOT-33, 0-100								
Healthcare costs (HUQ)								
Number of visits								
Physiotherapist								
General practitioner								
Allied health professional								
Complementary care provider								
Emergency department								
Medical specialist								
Admitted to the hospital								
Hip surgery								
Other healthcare providers								
Healthcare Costs (HUQ)								
Medicine usage								
Prescription 1								
Prescription 2								
Prescription 3								
Productivity Costs (IPCQ)								
Indirect costs								
Absenteeism								
Presenteeism								
Productivity loss								

QALY: Quality Adjusted Life Years. HUQ: Health care utilization questionnaire. IPCQ: The Productivity Costs Questionnaire. iHOT-33: International Hip and Outcome Tool 33. SD: Standard Deviation. 95% CI: 95% Confidence Interval. DKK: Danish Crowns.

**Table 5.** Incremental Cost-Effectiveness Ratios (ICERs), Incremental Cost-Utility Ratios (ICURs), and Distribution of the Joint Cost-Effect Pairs in the Cost-Effectiveness (CE) Plane.

Analysis	Mean cost difference (95% CI)	Mean effect difference (95% CI)	ICUR/ICER	Distribution in CE Plane (%)			
				NE	SE	SW	NW
Main analysis							
iHOT-33							
QALYs							
SA 1: Complete case analysis							
iHOT-33							
QALYs							
SA 2: Imputed data sets							
iHOT-33							
QALYs							
SA 3: Excluding Melbourne							
iHOT-33							
QALYs							

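### Hip-surgery costs are taken from the patient-reported HUQ and imputed when it is missing, and the trial's own record of who was operated on is never linked to the costing

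*SAP*

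**What the plan says.** SAP, Measurement of costs: the exercise programme is micro-costed. For the rest, "Costs of usual care and other costs in the supervised strength exercise group will be measured using the HUQ questionnaire", with the iPCQ for productivity. No other source is named for healthcare use outside the programme.

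SAP, Healthcare utilization questionnaire (HUQ): healthcare and medication use is "measured by a nine-item patient-reported cost questionnaire (HUQ"). Its content includes hospital admissions and medical procedures. In Table 4, hip surgery is a row in the block headed "Healthcare costs (HUQ").

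SAP, Base-case cost-effectiveness and cost-utility analysis: missing data are imputed by chained equations with predictive mean matching, and "Cost and effect data will be assumed to be missing at random". Predictors are chosen by a general rule (baseline imbalance, relation to missingness, association with outcome). Recorded surgery is neither named nor excluded.

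SAP, Hip surgery (a secondary outcome): "The number of patients undergoing hip surgery in each intervention group will be recorded throughout the study" and registered at 3, 6 and 12 months. This spans the 12-month horizon of the economic evaluation.

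SAP, Dropouts: "There is a risk of dropout in both groups if the treatment results in insufficient improvement of symptoms". The same section lets dissatisfied patients have a further consultation with the surgeon.

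**The concern.** The SAP fixes a self-reported questionnaire as the source for what may be one of the larger healthcare costs per patient, and it leaves unused a record of the same event that the trial already keeps. Where the HUQ is missing but the operation is on record, the base case would estimate something the trial knows. If the imputation ignores surgery, donors are mostly patients who were not operated on, because operations are likely to be the minority. The complete-case sensitivity analysis cannot reveal the problem, since by definition it leaves the patient out. The analysis without Melbourne keeps the same cost source.

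At stake are the incremental cost, the ICER and the ICUR, and so the second stated hypothesis (cost-effectiveness at 12 months). The primary iHOT-33 comparison is not affected.

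**Working it through.** **Text check.** The SAP states no figure on this point, so there is nothing to reproduce. Set side by side, Measurement of costs and Table 4 name the HUQ as the source for surgery, the base-case section imputes missing costs, and the Hip surgery section keeps a separate record over the same 12 months. No section joins the last to the first two.

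**Illustration of size.** The inputs are assumptions, because the SAP gives no surgery rate, unit cost of surgery or HUQ return by surgery status.

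- p: true 12-month surgery rate in an arm. Pairs used: 20% vs 10%, 15% vs 5%, 10% vs 5%.
- m1: HUQ missing among operated patients, 30-50%.
- m0: HUQ missing among other patients, 15-22%.
- The HUQ is treated as wholly present or absent, and the imputation does not condition on surgery. It then reproduces the surgery rate among those who returned the HUQ:

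rate carried into costs = p(1 - m1) / [p(1 - m1) + (1 - p)(1 - m0)]

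Worked example, m1 = 50%, m0 = 15%:

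- p = 10%: 0.10 × 0.50 / (0.10 × 0.50 + 0.90 × 0.85) = 0.050 / 0.815 = 6.1%
- p = 5%: 0.05 × 0.50 / (0.05 × 0.50 + 0.95 × 0.85) = 0.025 / 0.8325 = 3.0%
- Difference carried: 3.1 points against a true 5 points, so 63% is retained.

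Share of the true between-arm difference retained:

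| True rates | m1 30%, m0 15% | m1 30%, m0 22% | m1 50%, m0 15% | m1 50%, m0 22% |
|---|---|---|---|---|
| 20% vs 10% | 87% | 93% | 67% | 72% |
| 15% vs 5% | 85% | 92% | 64% | 69% |
| 10% vs 5% | 85% | 91% | 63% | 68% |

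Retention is 63-93%, a loss of 7-37%. In counts this is about 0.3 to 2.2 operations per 60 patients.

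**Cross-check on a second set of assumptions.** Overall HUQ missingness is set at 21.7%, which is (120 - 94)/120 from the SAP's sample sizes, or at 28%, its stated dropout allowance. Operated patients are one, two or three times as likely as others to miss the HUQ. The true difference is 6 operations per 60 (15% vs 5%, or 20% vs 10%).

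- Equally likely: 6.0 carried, no loss.
- Twice as likely: 4.9-5.2 at 21.7% missing, 4.5-4.8 at 28%.
- Three times as likely: 4.2-4.7 and 3.4-4.2. The worst case is a loss of (6 - 3.44)/6 = 43%.

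With 10% surgery in both arms and the same missingness, the between-arm error is zero in every case.

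**The case against.** The strongest reply is that the attenuation depends on an imputation model without surgery, while the SAP's predictor rule admits variables related to missingness or to the outcome. If surgery drives both, a careful analyst would include it, and matching would then favour operated donors. This stands as far as it goes: the rule could admit surgery. It does not require it, however, and even a good model would still impute an event that is on record.

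Second, differential non-response is not in the documents. The Dropouts section ties dropout to insufficient improvement, not to surgery. The Withdrawal/follow-up section has patients who withdraw still asked for assessments even if they have surgery, and the Missing data section promises an attempt to collect data from every randomised participant. This stands: higher non-response in operated patients is plausible but assumed.

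Third, the surgery record may be less independent than it looks. The Hip surgery section counts patients operated on. It gives no data source and no cost, and its registration times coincide with the questionnaire follow-ups. If both rely on the same contact, both may be missing together. This also stands, and it limits what the record can repair.

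A reader might infer that the trial knows every operation and its cost, or that avoided surgery is necessarily understated to the disadvantage of the exercise arm. The documents support neither: the record is of patients, not costs, and the SAP does not say which arm will have more surgery.

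**Conclusion.** The point holds as a weakness in the stated method. The SAP names the weaker source for surgery cost, imputes when that source is missing, and does not use its own surgery record, which covers the full economic horizon.

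The size is conditional. If operated patients return the HUQ less often and the imputation ignores surgery, about 7-37% of the between-arm surgery-cost difference is lost on the main set of assumed rates, and up to 43% at the extreme of the second set. There is no loss if non-response is unrelated to surgery, or if surgery rates and missingness are the same in both arms. The sign of the resulting error in incremental cost depends on which arm has more operations.

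The SAP contains no contradiction here, and the illustration does not show that bias will occur. The case for change is that a better use of data already collected is available at little cost.

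**What to change.** - **Measurement of costs and Table 4:** state that hip-surgery resource use comes from the trial's surgery record, reconciled with the HUQ, and is costed as event times unit cost wherever surgery status is known. State the source of the record and change the source shown for the hip-surgery row.
- **Base-case analysis:** name recorded surgery (yes/no and interval) as a predictor in the imputation model for the remaining HUQ and iPCQ components. Impute surgery only for patients whose status is unknown for the interval. A rule that surgery is never imputed would be unsound, because patients lost to follow-up without surgery information would be counted as not operated on.

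The cost is a few sentences in the SAP and one data merge; the surgery data are already planned. The downside is that the surgery component then has a different source from the other healthcare costs, which should be noted under Table 4.
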